8.3.1.2 Revised Upper Limb Model (RULM)

Background

RULM is a validated, SMA-specific assessment that measures motor performance in the upper limbs from childhood through adulthood in ambulatory and never ambulatory individuals with SMA, and weaker individuals who have a floor effect or very low score on the Hammersmith Functional Motor Scale (HFMS) ([Mazzone et al 2017](#)). The revised version of the test consists of 19 scorable items: 18 items scored on a 0 (unable) to 2 (full achievement) scale, and one item that is scored from 0 (unable) to 1 (able). These item scores are summed to give a total score ranging from 0 to 37 points with lower scores reflecting poorer ability. The RULM consists of upper limb performance items that are reflective of reachable space and activities of daily living (i.e., raise a can to mouth as if drinking, take a coin and place it in a box, and remove the lid of a container). The test is performed unilaterally using the limb preferred by the patient. The RULM is quickly administered and suitable for use in multicenter settings. Evaluation of inter-rater reliability and test-retest reliability demonstrated that these functional assessments can be performed reliably in a multicenter clinical trial with rigorous initial, annual, and periodic retraining and support to ensure standardization. The RULM will be administered by a site clinical evaluator (e.g., licensed physical or occupational therapist, or national equivalent) in accordance with the Schedule of Assessments.

The RULM was a critical motor assessment that contributed to risdiplam approval by the Food and Drug Administration (FDA) in the SUNFISH trial which included 2 to 25 year old Type 2 and Type 3 SMA patients ([EVRYSDI Prescribing Information 2020, Genentech 2021](#)). The RULM was used in the CHERISH clinical trial of nusinersen which included Type 2 and 3 SMA in 2 to 12 year olds ([Mercuri et al 2018b](#)). In the CHERISH study, the least squares mean analysis of the RULM data versus controls showed 3.7 point difference (95% CI = 2.3 – 5.0). Since the RULM was a secondary endpoint in the CHERISH trial and a hierarchical end point analysis was performed, a p-value was not calculated since a prior endpoint did not reach statistical significance. Like the HFMSE, the RULM has been successfully implemented in clinical trials that assess efficacy of SMN-targeting therapies. RULM administration is recommended for assessment of patients > 2 years of age with the ability to sit by the SMArtCare-project ([Pechmann et al 2019, Schorling et al 2020](#)).

Completion of Assessment

Obtaining a complete RULM assessment at a visit that is a true representation of the participant's motor ability is critical in order to appropriately investigate OAV101 efficacy. Every effort should be made to administer all scale items appropriately following scale criteria. In the event that an item is not able to be administered a 'Cannot Test' (CNT) is marked for that item. To ensure the patient's true motor ability is being represented, rescheduling of the assessment administration is warranted when any factor significantly impedes the participant's ability to perform the motor assessment which includes behavior issues (e.g., tantrums, inconsolable), refusal to participate in testing, transient pain, fractures, intercurrent surgery, or recent pneumonia or other infections. [CCI](#)

Study specific requirements around RULM administration requirements are outlined below. Ensuring completeness of the assessment is an approach to ensure that data

8.3.3.4 CCI

CCI

[REDACTED]

8.3.3.5 CCI

CCI

[REDACTED]

CCI

[REDACTED]

8.3.3.6 CCI

CCI

[REDACTED]

8.3.3.7 CCI

CCI

[REDACTED]

8.4 Safety

Safety assessments are specified below with the assessment schedule detailing when each assessment is to be performed ([Table 8-1](#)). Safety parameters include demographics/medical history, physical and neurological examinations, vital signs, height and weight measurements, 12-lead ECGs, echocardiograms, laboratory assessments, and AE monitoring. For details on AE collection and reporting, refer to [Section 10.1](#).

As per [Section 4.6](#), during a Public Health emergency as declared by Local or Regional authorities i.e., pandemic, epidemic or natural disaster, that limits or prevents on-site study visits, regular phone or virtual calls can occur for safety monitoring and discussion of the participant's health status until it is safe for the participant to visit the site again. If participants cannot visit the site for safety lab assessments through central labs, home-nursing may be deployed using central lab kits or local lab collection may be used and results will be entered in the eCRF.

8.4.1 Laboratory evaluations

A central laboratory will be used for analysis of all specimens collected unless otherwise specified. Details on the collections, shipment of samples and reporting of results by the central laboratory are provided to Investigators in the Laboratory Manual.

For countries where regulatory requirements do not permit Point of Care Testing for urinalysis (i.e., use of dipstick) the analysis will be performed at the central laboratory.

8.4.1.1 Urinalysis

Dipstick measurements for protein, blood, and WBC/leukocytes will be performed. If dipstick measurement results are positive (abnormal), a urine sample will be sent to the central laboratory for microscopic evaluation in accordance with the Laboratory Manual.

8.4.1.2 Hematology

Hematology analysis will include a complete blood count with differential and platelet count. Samples will be collected and shipped in accordance with the laboratory manual provided by the central laboratory. Blood samples for hematology analysis will be collected as specified in the [Table 8-1](#).

Hematology analysis will include the following at all trial visits:

- Hematocrit
- Hemoglobin
- MCH
- MCHC
- MCV
- Platelets
- Red blood cells
- White blood cells
- Differential (Basophils, Eosinophils, Lymphocytes, Monocytes, Neutrophils, Bands)

Transient decreases in platelet counts, some of which met the criteria for thrombocytopenia, were observed in OAV101 clinical studies with intravenous administration. In most cases, the lowest platelet value occurred the first week following OAV101 administration. Platelet counts should be obtained before OAV101/sham administration and should be closely monitored in the first two weeks following treatment on a regular basis afterwards as specified in [Table 8-1](#), until any abnormal platelet counts return to baseline.

Hematology analyses are required prior to discharge on Day 2 and Week 52+2 Days. These tests will be performed as per investigational site standard procedures at the local laboratory. As determined by the Investigator, further hematology tests should be done in the first two weeks following OAV101 administration as per investigational site standard procedures at the local laboratory. Local labs should be entered on the respective eCRF page.

Investigators will receive hematology results from all other study visits from the central laboratory.

8.4.1.3 Coagulation panel

Coagulation testing will include prothrombin time (PT), international normalized ratio (INR), and activated partial thromboplastin time (aPTT). Coagulation testing is required to be done locally to confirm that there are no clinically significant abnormal results prior to OAV101 dosing/sham procedure (both Treatment Period 1 and 2).

8.4.1.4 Clinical chemistry

Samples will be collected and shipped in accordance with the laboratory manual provided by the central laboratory. Blood samples for chemistry analysis will be collected as specified in the Assessment Schedule ([Table 8-1](#)). Clinical chemistry may be evaluated in the non-fasted state.

If immediate/same-day chemistry analyses are required during Treatment Period 1 or Treatment Period 2, as determined by Investigator, tests will be performed as per investigational site standard procedures at the local laboratory. **If liver aminotransferase elevations occur post OAV101 administration/sham procedure, the process outlined in [Section 10.3.1](#) should be followed.**

Chemistry analysis will include the following analytes:

- Albumin
- Alkaline phosphatase (ALP)
- Alanine aminotransferase
- Aspartate aminotransferase
- GGT
- Lactate Dehydrogenase (LDH)
- Glutamate dehydrogenase
- Bicarbonate
- Calcium
- Phosphorus
- Chloride

- Sodium
- Potassium
- Creatinine
- Creatine kinase
- Total Bilirubin (NOTE: If the total bilirubin concentration is increased above 1.5 times the upper limit of normal, direct and indirect reacting bilirubin should be differentiated)
- Direct Bilirubin
- Indirect Bilirubin
- Blood urea nitrogen
- Glucose

Troponin I will be collected as specified in the Schedule of Assessments ([Table 8-1](#)).

CCI

8.4.1.5 BLOOD: Serum beta-human chorionic gonadotropin pregnancy test (Quantitative). Female participants only

Blood beta-human chorionic gonadotropin (beta-hCG) testing (Quantitative) will be performed at screening visit 2 and at the Week 48 visit. Serum beta-hCG testing will be performed on females of childbearing potential (See [Section 8.4.2](#)).

8.4.1.6 URINE beta-human chorionic gonadotropin pregnancy test (Qualitative). Female participants only

All female participants who are sexually active or have reached menarche will have pregnancy testing. Additional pregnancy testing might be performed if requested by local requirements. The cultural differences as well as standard of care approaches across participating countries must be taken into account in order to appropriately manage contraception and pregnancy considerations.

Urine human chorionic gonadotropin (hCG) dipstick testing will be performed on females of child-bearing potential. First-morning urine is the preferred specimen; however, any specimen is suitable for testing.

8.4.2 Pregnancy testing

For female participants who are sexually active or have reached menarche, quantitative beta-human chorionic gonadotropin testing in blood for pregnancy is required at screening visit 2 and at the Week 48 visit. For all female participants meeting this definition of child-bearing potential, qualitative beta-human chorionic gonadotropin in urine will be performed at monthly intervals during the trial. Note that a positive urine test should be confirmed with a serum pregnancy test. The cultural differences across participating countries need to be taken into account and it is acceptable to have both options simultaneously in the protocol to allow for cultural differences between participating countries. In case of a positive test, the participant

must contact the investigator immediately. In this fashion, the pregnancy discussion will become an additional point at each visit, serving to increase compliance with contraception.

*Additional pregnancy testing may be performed if requested per local requirements.

8.4.3 Clinical safety evaluations

8.4.3.1 Neurological examination

A complete neurological examination is performed at visits specified in [Table 8-1](#), with attention to exam features and patient symptoms consistent with a sensory neuronopathy. The neurological exam should include detailed, age-appropriate sensory testing (such as examination of proprioceptive, vibratory, tactile and pain sensation) at each visit. An age-appropriate sensory exam is important for sensory neuronopathy detection.

Any clinically significant abnormal finding should be recorded as an AE. The neurological examination should only be recorded as abnormal if there are abnormalities in the sensory examination.

Further clinical evaluation of sensory abnormalities will include nerve conduction studies per local standard of care including but not limited to sural sensory nerve action potential (SNAP).

8.4.3.2 Physical examination

Physical examinations will be conducted by the investigator or designee as specified in [Table 8-1](#).

A complete review of systems is performed at the time of each physical examination. Physical examinations will include each system: head, eyes, ears, nose and throat (HEENT), lungs/thorax, cardiovascular, abdomen, musculoskeletal, neurologic, dermatologic, lymphatic, and genitourinary.

Physical examination data will be captured on source documentation.

8.4.4 Vital signs

Vital sign parameters include blood pressure, respiratory rate, pulse, temperature, and pulse oximetry.

Vital signs will be obtained as specified in the [Table 8-1](#). On Day 1 and Week 52+1 Day (OAV101 administration or sham procedure), vital signs, with the exception of blood pressure, will be recorded pre-dose and then monitored every 15 (\pm 5) minutes for the first 1 hour, every 30 (\pm 10) minutes until 2 hours, every 2 hours (\pm 15 minutes) until 8 hours, and every 4 hours (\pm 30 minutes) until 16 hours. Blood pressure will be recorded pre-dose and every 8 hours (\pm 2 hours) through 16 hours.

8.4.5 Electrophysiology

Electrophysiology assessments are performed in conjunction with patient history and neurological examination to monitor for sensory neuronopathy.

8.4.5.1 Sensory nerve action potential (SNAP)/electrophysiology

BACKGROUND

The sensory nerve action potential (SNAP) provides information on the sensory nerve axon and its pathway from the distal receptors in the skin to the dorsal root ganglia. The SNAP represents the sum of single nerve fiber action potentials.

PERFORMANCE

Although electrophysiology (SNAP assessment) is performed at Screening and at post-treatment visits when there are sensory abnormalities in the neurological examination detailed investigations for a sensory neuronopathy can be initiated based on the clinical judgement at any time during the study.

Orthodromic or antidromic SNAPs are acceptable depending on the institutional protocol. Sensory nerve conduction studies to assess SNAPs will be performed for all study patients at Screening. The SNAP will be scored as “Present” or “Absent” or “Unable to obtain”.

Pre-treatment: SNAP must be performed for all participants at Screening Visit 1. If the SNAP is scored as “Unable to obtain” at Screening Visit 1, then SNAP must be performed at Screening Visit 2. Bilateral radial and sural nerve SNAPs must be obtained at one of the two screening visits for trial eligibility. Rescheduling is warranted when any factor impedes the ability to obtain SNAP data.

If the SNAP is scored as “Absent” at any one of the pre-treatment visits, the clinician must assess whether the absent SNAP is supported by any clinically significant sensory abnormal finding(s) in the neurological examination.

Post-treatment: Post-treatment, SNAP is performed if there are sensory abnormalities in the neurological examination. A complete neurological examination is performed at visits specified in [Table 8-1](#), with attention to exam features and patient symptoms consistent with a sensory neuronopathy (refer to [Section 8.4.3.1](#)).

Any patient with new post-treatment sensory symptoms with or without loss of a SNAP will receive a comprehensive assessment of the differential diagnosis. The differential diagnosis should include a careful assessment for sensory neuronopathy (sensory ganglionopathy). CSF testing and MRI imaging of brain, spinal cord, and dorsal root ganglia is encouraged. Sensory ganglionopathies are usually associated with diffuse SNAP abnormalities but may be patchy early, with upper limb involved before lower limb.

TECHNICAL REQUIREMENTS

Performance of sensory nerve action potentials (SNAPs) should comply with professional society standards ([Stålberg et al 2019](#), [AANEM 2020](#)).

SNAP is a conduction study commonly used to evaluate suspected peripheral neuropathies.

Nerve conduction study is a test commonly used to evaluate the function, especially the ability of electrical conduction by the motor and sensory nerves of human body. It is evaluated by performing sural SNAP. The sural SNAP is obtained by electrically stimulating sensory fibers. Results will be entered in the eCRF.

8.4.6 Anthropometry

Complications associated with SMA (e.g., scoliosis and contractures) are considered in the determination of height, weight, and BMI.

8.4.6.1 Body height (segmental by tibial length)

Direct measurement of recumbent length or height may be challenging in children and adolescents with physical disabilities due to joint contractures, muscular weakness, scoliosis, or poor cooperation. Since patients in the trial are never ambulatory, use the tibial length for segmental height assessment in all participants ([Preedy 2012](#), [Samson-Fang and Bell 2013](#), [Mokhy et al 2020](#)). Tibial length measurement does not require specialized equipment, is not impacted on by knee and ankle contractures and the landmarks are relatively easy to palpate.

- Use a flexible tape measure that does not stretch.
- Tibial length is the distance from the superomedial edge of the tibia to the inferior edge of the medial malleolus.
- The measurement should be conducted with the child in a seated position facing the observer with the left ankle or calf resting on the right knee so that the medial aspect of the tibia faces upwards. Measurements are recorded in centimeters (cm).

Use the following equation for both males and females to estimate height in males and females who are ≥ 2 to ≤ 12 years of age (Stevenson Equation).

- Height = $(3.26 \times TL) + 30.8$
 - TL=Tibial length

Use the following equations for males and females to estimate height in males and females who are > 12 years of age (Gauld Equation).

- Males: Height = $(2.758 \times TL) + (1.717 \times A) + 21.818$
- Females: Height = $(2.771 \times TL) + (1.457 \times A) + 37.748$
 - TL = Tibial length (cm)
 - A = age in years to one decimal place (e.g. 5.3 years)

The height calculation is necessary to calculate BMI, an eligibility criterion that must be assessed at screening. The height calculation should be checked by an additional study staff to ensure accuracy.

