 - An active infectious process requiring systemic therapy intended to eliminate the infection within 30 days prior to dosing of OAV101 or the sham procedure
 - An active but untreated viral or bacterial infectious process within 30 days prior to dosing of OAV101 or the sham procedure
 - Febrile illness within 30 days prior to OAV101 administration or sham procedure
8. Administration of vaccines within 2 weeks prior to injection of OAV101 or sham procedure.
9. Clinical or radiological signs of aspiration within 30 days prior to Day 1.
10. Requiring invasive ventilation, awake noninvasive ventilation for > 6 hours during a 24-hour period, noninvasive ventilation for > 12 hours during a 24-hour period or requiring tracheostomy within 30 days prior to Day 1.

11. Awake hypoxemia (defined as O₂ saturation < 95% in room air) within 30 days prior to Day 1.
NOTE: For altitudes > 1000 m, awake hypoxemia is defined as O₂ saturation < 92% in room air
NOTE: For altitudes > 2500 m, awake hypoxemia is defined as O₂ saturation < 90% in room air
12. Hepatic dysfunction (i.e., ALT, TBL, GGT or GLDH, > ULN (i.e., CTCAE grade 1 or greater)) at Screening Visit 1.
NOTE: In the absence of other liver laboratory abnormalities, isolated AST elevation is not considered exclusionary
13. Complications at screening that would interfere with motor efficacy assessments including but not limited to:
 - Presence of severe contractures (e.g., hip flexion contracture) which limits the participant's ability to be positioned in prone for HFMSE item administration
 - Scoliosis with a Cobb angle > 40 degrees in a sitting position, evident on x-ray examination at Screening
14. BMI < 3rd percentile if considered clinically significant by the investigator
NOTE: BMI is based on the WHO Child Growth Standards ([WHO 2022a](#)) and WHO Growth reference data for 5-19 years ([WHO 2022b](#)).
15. History of untreated or uncorrected vitamin deficiencies which can produce sensory neuropathies such as pyridoxine deficiency (B6).
16. Concomitant use of any of the following medication categories within 90 days prior to study treatment (Day 1):
 - Ongoing systemic immunosuppressive therapy (e.g., corticosteroids (except for prophylactic use for OAV101 dosing), cyclosporine, tacrolimus, methotrexate, cyclophosphamide, intravenous immunoglobulin, rituximab), plasmapheresis, immunomodulators (e.g., adalimumab)
17. Inability to tolerate corticosteroids administered by mouth or gastrostomy tube.

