- **RULM**: Baseline value for RULM total score is defined as the average of all non-missing assessments prior to the first administration of study treatment during Treatment Period 1, assuming all assessments have complete and valid total scores available. If two of the assessments have a complete and valid total score available, then the baseline RULM total score is defined as average of the two available assessment scores. If just one of the assessments has a complete and valid total score available, then the baseline RULM total score is defined as the single total score available.
- **Other assessments**: The latest non-missing measurement or evaluation made prior to the first administration of study treatment during Treatment Period 1.

Change from baseline is defined as post-baseline value minus baseline value.

For HFMSE and RULM, the **End of Follow-up Period 1** assessment is defined as the average of the Week 48 and Week 52 assessments, assuming both assessments have complete and valid total / individual scores available. If just one of the assessments collected at these two visits has a complete and valid total / individual score available, then the end of Follow-up Period 1

assessment is defined as the single assessment total / individual score collected at Week 48 or Week 52.

Last participation day can be calculated using end of participation date – date of second administration of study treatment + 1.

Inexact values will be handled as follows.

- If a laboratory value is recorded/reported as “>X”, “≥X”, “- If an antibody titer value is reported as <12.5, a value of 0.5×12.5 will be used and if ≥ 819200 is reported, a value of 1.5×819200 will be used for analysis purposes. The originally recorded values will be displayed in corresponding listings.

An **Adverse Event** (AE) is any untoward medical occurrence in a clinical investigation participant, which does not necessarily have a causal relationship with the drug or device under study.

A Treatment Emergent Adverse Event (TEAE) is any AE whose onset or worsening occurred after dosing on Day 1 till the end of follow-up period 2.

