2.7.4.3 Anthropometry

Anthropometry will be assessed at the scheduled visits in accordance with the Schedule of Study Assessments. All data will be summarized using the SAF.

Observed values as well as change from baseline values through the end of Follow-up Period 1 will be summarized at each scheduled visit for body height as derived from tibial length, weight, and BMI.

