5.6 Clinically significant vital sign values

Vital sign results will be flagged as clinically significant if they meet the pre-specified criteria which are defined as follows.

Systolic and Diastolic Blood Pressure:

- For participants aged <18 years at the time of assessment, diastolic and systolic blood pressure values greater than or equal to the corresponding to the 90th percentile value for age, gender, and height will be used to classify 'high' clinically significant values. The relevant values are contained in Table 4 (BP Levels for Boys by Age and Height Percentile) and Table 5 (BP Levels for Girls by Age and Height Percentile) of Flynn 2017.
 - Participants aged ≥ 2 to <3 years at the time of assessment will utilize the blood pressure levels defined for age 2 years, participants aged ≥ 3 to <4 years at the time of assessment will utilize the blood pressure levels defined for age 3 years, etc.

- Height percentile will be defined using the height at the time of assessment, or the most recently recorded height prior to the assessment if the height at the time of assessment is not available. Participants with a height which falls between two percentiles will be classified according to the lower of the two percentiles. For example, if a girl participant aged 2 years at the time of assessment has a height of 90.0cm, they would fall between the 25th percentile for height (88.6cm) and the 50th percentile for height (91.1cm). In this case, the participant would be considered to belong in the 25th percentile for height and the 90th percentile for blood pressure according to that 25th percentile for height will be utilized for classification purposes.
- For participants aged 18 years and above at the time of assessment, systolic blood pressure values ≥ 120 mmHg and diastolic blood pressure values ≥ 80 mmHg will be classified as 'high' clinically significant values.
- For all participants regardless of age at assessment, systolic blood pressure values below the 5th percentile will be classified as 'low' clinically significant values. The 5th percentile value can be estimated using the following formula: 70 mmHg + (2*participant's age in years).

Temperature:

- For participants <18 years at the time of assessment, temperature values $\geq 38.4^{\circ}\text{C}$ will be classified as 'high' clinically significant.

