- For participants ≥ 18 years at the time of assessment, temperature values $\geq 39.1^{\circ}\text{C}$ will be classified as 'high' clinically significant.
- For all participants regardless of age at assessment, temperature values $\leq 35^{\circ}\text{C}$ will be classified as 'low' clinically significant.

Pulse rate:

The criteria for classifying high and low pulse rate values are contained in the table below (Flemming 2011).

Age at assessment	High (bpm)	Low (bpm)
2 to <3 years	>128	<92
3 to <4 years	>123	<86
4 to <6 years	>117	<81
6 to <8 years	>111	<74
8 to <12 years	>103	<67
12 to <15 years	>96	<62
15 to <18 years	>92	<58
≥ 18 years	≥ 120 with increase from updated baseline ¹ of ≥ 15 bpm	≤ 50 with decrease from updated baseline ¹ of ≥ 15 bpm

¹Updated baseline is the last value collected before the participant's 18th birthday.

Weight

- For participants <18 years at the time of assessment, weight values which reflect an increase from baseline of ≥ 2 BMI-for-age percentile categories will be classified as 'high' clinically significant; weight values which reflect a decrease from baseline of ≥ 2 BMI-for-age percentile categories will be classified as 'low' clinically significant.
 - Baseline BMI-for-age weight status categories are underweight (less than the 5th percentile), healthy weight (5th percentile to less than the 85th percentile), overweight (85th to less than the 95th percentile) and obese (equal to or greater than the 95th percentile).
 - BMI-for-age percentile categories (P1 to P99) are obtained from the WHO Growth Charts (For ≥ 5 years: [\[https://www.who.int/tools/growth-reference-data-for-5to19-years/indicators/bmi-for-age\]](https://www.who.int/tools/growth-reference-data-for-5to19-years/indicators/bmi-for-age), For <5 years: [\[https://www.who.int/toolkits/child-growth-standards/standards/body-mass-index-for-age-bmi-for-age\]](https://www.who.int/toolkits/child-growth-standards/standards/body-mass-index-for-age-bmi-for-age) [\[https://www.who.int/toolkits/child-growth-standards/standards/body-mass-index-for-age-bmi-for-age\]](https://www.who.int/toolkits/child-growth-standards/standards/body-mass-index-for-age-bmi-for-age)).

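### A participant who passes age 12 on study changes height equation, and the jump between equations is tabulated as change in height and BMI; the printed constants above 12 should also be checked

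*Protocol*

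**What the plan says.** Protocol 8.4.6.1 gives three equations (TL = tibial length in cm, A = age in years):

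- Age 2 to 12, both sexes: 3.26 x TL + 30.8.
- Above 12: "Use the following equations for males and females to estimate height in males and females who are > 12 years of age". Males: 2.758 x TL + 1.717 x A + 21.818. Females: 2.771 x TL + 1.457 x A + 37.748.

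The same section notes: "The height calculation is necessary to calculate BMI, an eligibility criterion that must be assessed at screening". The criterion itself is "BMI < 3rd percentile if considered clinically significant by the investigator" (Protocol 5.2, criterion 14), and Protocol Section 3 repeats it as criterion 10 for Period 2.

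SAP 2.1.1 states that change from baseline "is defined as post-baseline value minus baseline value". SAP 2.7.4.3 has observed values and changes "summarized at each scheduled visit for body height as derived from tibial length, weight, and BMI", through the end of Follow-up Period 1. Two flags in SAP 5.6 also depend on height. For blood pressure, "Height percentile will be defined using the height at the time of assessment". Below age 18, the weight flag picks out "weight values which reflect an increase from baseline of" two or more BMI-for-age percentile categories, or a decrease of that size.

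Neither document has a rule for a participant who passes 12 between two measurements, and neither comments on the difference between the sex-specific constants.

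**The concern.** A change from baseline is interpretable only if both values come from the same measuring rule. Here the rule switches at 12, and nothing makes the equations meet at that age. A child who turns 12 during the year can therefore appear to shrink, or to grow by more than 10 cm, because of the formula alone. These figures would stand in a safety table on growth, in a trial where the active arm also receives prednisolone.

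The second issue is the size of the sex gap just above 12. Up to 12 it is zero by construction. At 12.1 years it is about 13 cm, with the boy lower. If one of the constants were wrong, absolute heights and BMIs above 12 would be wrong for that sex, and some blood-pressure height percentiles might be.

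**Working it through.** **Inputs.** All coefficients are as printed in Protocol 8.4.6.1. The documents give no tibial lengths, so 28 to 40 cm is assumed, with 22 to 42 cm as a wider check. The plan states no height difference or step, so it has no figure to reproduce first.

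**1. Step at 12 with an unchanged leg** (equation for above 12 at A = 12.1, minus the equation for up to 12):

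| TL (cm) | up to 12 | male, 12.1 | female, 12.1 | step, boy | step, girl |
|---|---|---|---|---|---|
| 28 | 122.08 | 119.82 | 132.97 | -2.26 | +10.89 |
| 34 | 141.64 | 136.37 | 149.59 | -5.27 | +7.95 |
| 40 | 161.20 | 152.91 | 166.22 | -8.29 | +5.02 |

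**2. A growing child**, TL 34 to 35 cm, age 11.6 to 12.6.

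- Baseline: 3.26 x 34 + 30.8 = 141.64.
- Boy at follow-up: 2.758 x 35 + 1.717 x 12.6 + 21.818 = 139.98, change -1.66 cm.
- Girl at follow-up: 2.771 x 35 + 1.457 x 12.6 + 37.748 = 153.09, change +11.45 cm.
- Younger equation at both visits: 3.26 x 1 = +3.26 cm.
- Older equation at both visits: boy 2.758 + 1.717 = +4.48 cm; girl 2.771 + 1.457 = +4.23 cm.

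Either single equation gives a gain of 3.3 to 4.5 cm. Only the switch produces -1.7 or +11.5 cm.

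**3. BMI change for the same child at a constant 30 kg.** Baseline: 30/1.4164² = 14.95. Boy: 30/1.3998² = 15.31, change +0.36. Girl: 30/1.5309² = 12.80, change -2.15. Younger equation at both visits: 30/1.4490² = 14.29, change -0.67 (unrounded values). The switch reverses the sign for the boy and about triples the fall for the girl.

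**4. Sex gap above 12.** The constants differ by 37.748 - 21.818 = 15.93 cm. Girl minus boy at equal TL and age = 0.013 x TL - 0.260 x A + 15.93.

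- A = 12.1: 13.15 (TL 28) to 13.30 (TL 40).
- A = 17.9: 11.64 (TL 28) to 11.80 (TL 40).
- TL 22 to 42, both ages: 11.56 to 13.33.

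The range of 11.6 to 13.3 cm therefore hardly depends on the assumed tibia. At equal weight, the boy's BMI comes out 15 to 23% above the girl's (TL 28 to 40).

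**5. What a wrong constant would affect.** Within the equations for above 12, height change is 2.758 x dTL + 1.717 x dA (male) or 2.771 x dTL + 1.457 x dA (female), so the constant cancels. BMI change is different, because height enters squared in the denominator. As an illustration, take a boy with TL 34 to 35, age 12.1 to 13.1, a constant 30 kg, and the male constant raised by the whole 15.93 cm. As printed, heights are 136.37 and 140.84, BMI goes from 16.13 to 15.12, change -1.01. Shifted, heights are 152.30 and 156.77, BMI goes from 12.93 to 12.21, change -0.73. With 30 to 33 kg instead, the change moves only from 0.50 to 0.49. The effect depends on the weight change.

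**The case against.** The strongest objection to the first part is that neither document says the equation is chosen by age at each measurement. If programming fixed it at screening age, there would be no step. That is true. However, the protocol assigns equations by age with no reference date, and the older equations take current age as an input, so age at measurement is the natural reading. It remains an assumption.

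On the constants, each is printed once and nothing elsewhere contradicts it. A reader might infer a misprint. The documents do not support that: separately fitted equations can have different intercepts, the cited sources are not available here, and a digit may have been misread in text conversion. Two arguments that might seem to strengthen the inference carry little weight. Comparing the slope terms without the intercepts describes no child, because the two are fitted together. The age of 5.3 years given as an example in that section illustrates the number format and says nothing about a constant.

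A reader might also infer that every blood-pressure percentile above 12 would be wrong. That goes too far: SAP 5.6 assigns a height between two percentiles to the lower one, so an error need not change the category, and from age 18 the cut-off does not use height.

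The protocol has a second staff member check the height calculation. That would catch a slip in arithmetic, but not a wrong printed constant or the switch of equation.

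**Conclusion.** The step at 12 follows from the plan's own rules and needs no outside source. On the reading by age at measurement, participants who pass 12 between baseline and follow-up have a tabulated change that includes a formula artefact: -2.3 to -8.3 cm in boys and +10.9 to +5.0 cm in girls with an unchanged leg (TL 28 to 40 cm assumed). BMI change carries it too. The BMI-for-age weight flags may, but this cannot be computed because the reference tables are not in the documents.

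The 15.93 cm difference between the constants supports a check and nothing more.

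The consequences are limited. These outputs are descriptive, and HFMSE and RULM do not use height. Low BMI excludes only on the investigator's judgement, and SAP Section 4 says the study is fully enrolled. The documents do not give the number of participants who pass 12 or are above it, and randomisation should spread any artefact over both arms.

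**What to change.** 1. For participants who pass 12 between baseline and follow-up, add one supplementary display of change in height and BMI with a single named equation at both visits. Label it as an exception to the usual derivation, and note that one visit lies outside that equation's stated age range. State in the SAP that the main tables select the equation by age at measurement, if that is the intention; they otherwise stay as planned.

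2. Before the safety outputs are derived, compare the constants with the original protocol file, the cited source and the programmed version. If they are confirmed, record that and change nothing. If one is wrong, re-derive height, BMI and the dependent flags from the recorded tibial lengths. If this happens while Period 2 eligibility (criterion 10) is still being assessed, use the corrected height there too.

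The cost is one small table or listing and a formula check. A re-derivation is needed only if an error is found. No endpoint, main-table rule or settled Period 1 eligibility decision changes.
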